Specific Aims: Primary Aim #1: To determine the validity of the clinical prediction rule for identifying patients with neck pain who are likely to benefit from C-TJM. Pain and Disability. The investigators will examine the primary aim with separate random intercept linear mixed models with treatment group (MTE vs. MoE), status on the CPR (positive or negative) and time (baseline, 1-week and 4weeks) as fixed effects. The dependent variables will be pain (NPRS) and disability (NDI score). The hypothesis of interest is the group \* CPR status \* time interaction. The primary dependent variables are the 1-week NPRS and NDI scores to mirror the follow-up used in Cleland and colleagues' study. The investigators will assess the NPRS and NDI scores after 4 weeks to determine whether a patient's status on the rule predicts outcome at a longer follow-up. The investigators will perform planned pairwise comparisons at each follow-up period by using the Bonferroni test of inequality. The investigators hypothesize that patients who are positive on the rule and receive TJM will achieve greater improvement in immediate (1-week) and 4-week pain and disability, than patients who are negative on the rule and receive TJM, and compared to patients who are positive on the rule but receive an alternative exercise program without TJM. Because the rule is believed to be specific to a TJM intervention, investigators hypothesize that outcomes among those receiving the MoE treatment would not differ on the basis of a patient's status on the rule.

Secondary Aim #1: To compare the long-term (6-month) pain and disability scores (clinical

outcomes) and healthcare utilization based on status on the clinical prediction rule and the treatment received. The investigators will examine this with random intercept linear mixed models with treatment group (MTE vs. MoE), status on the CPR (positive or negative), and time (baseline and 6-months) as fixed effects. The dependent variables will be pain (NPRS) and disability (NDI) scores. The investigators will perform planned pairwise comparisons at each follow-up period by using the Bonferroni test of inequality. The hypothesis of interest is the group \* status on CPR \* time interaction. The investigators hypothesize that patients who are positive on the rule and received TJM would experience greater improvement at 6-months than patients who are negative on the rule and received the MoE program without TJM.

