Sample Size and Power. The sample size calculation is based on the primary aim of the study. This aim looks at the change in NDI at a 1-week follow-up as the dependent variable. The investigators based sample size calculation on detecting a statistically significant difference between any of the 4 cells of

the study which include the patient's status on the rule (patients that meet the CPR and patients that do not meet the CPR) and group (MTE and MoE) by using the 1-week NDI score at an alpha-level of 0.05. To maximize statistical power, investigators will aim to include 4 equal group sizes based on the rule status (positive vs. negative) and treatment (MTE vs MoE). Based on previous research investigators expect a standard deviation of change scores on the NDI of 12 points. To detect a 10 point change in NDI at the 1-week follow up (effect size 0.80) with 90% power using a two-tailed hypothesis and assuming a 50% distribution of patients who do and do not meet the rule based on our randomized block design, 31 patients per cell are required. The investigators will recruit 140 subjects into the study to control for dropouts prior to the 1- and 4-week follow-up and possible distribution discrepancies between the classifications. This will require recruitment of approximately 12 subjects per month over a 12-month recruitment period.

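### The primary time point is 1 week, but the stated test is a group × CPR × time interaction that effect modification at 4 weeks alone can satisfy

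*Combined protocol and SAP*

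**What the plan says.** All of this is in section 7.0 unless stated otherwise.

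- **Model.** Primary Aim #1 uses "separate random intercept linear mixed models with treatment group", CPR status and "time (baseline, 1-week and 4weeks) as fixed effects", one model for NPRS and one for NDI.
- **Test.** "The hypothesis of interest is the group" × CPR status × time interaction. The text does not say whether time is categorical, how many degrees of freedom the test has, or which visit it concerns.
- **Primary time point.** "The primary dependent variables are the 1-week NPRS and NDI scores to mirror the follow-up used in" a cited validation trial of a different rule. The 4-week data get a follow-on role, as a question about outcome further out: "The investigators will assess the NPRS and NDI scores after 4 weeks to determine whether a patient's status on the rule predicts outcome at a" […].
- **Other tests.** The plan adds "planned pairwise comparisons at each follow-up period by using the Bonferroni test of inequality".
- **Sample size.** "This aim looks at the change in NDI at a 1-week follow-up as the dependent variable". The target is a difference between any of the four cells.
- **Hypothesis.** The Synopsis, section 2.0 and Primary Aim #1 all predict that CPR-positive patients given TJM improve more at 1 week and at 4 weeks than each of two comparison cells.

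No criterion is written for concluding that the rule is valid.

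**The concern.** Validating a treatment-specific rule means showing that the MTE-versus-MoE difference depends on CPR status. With 1 week as the primary time point, the quantity needed is the difference of differences at 1 week. No test in the plan isolates it.

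The three-way interaction pools the two follow-up visits, so it can be significant because of 4 weeks alone. The pairwise comparisons do give results at 1 week, but each sets one cell against another. CPR-positive and CPR-negative patients within MTE can differ because the rule is merely prognostic. MTE and MoE within CPR-positive patients can differ because TJM helps everyone equally. Neither result shows effect modification.

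The two visits also answer different questions. TJM or mobilization is given only in sessions 1 and 2, and the later sessions follow the same exercise protocol in both arms. The 4-week measurement comes after two or three of those shared sessions: the treatment-session text places it at the start of visit 5, the schedule table at a separate 1-month follow-up. A signal seen only then is not the finding named as primary.

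**Working it through.** **Inputs from the documents.** SD of NDI change 12, difference 10 points, two-sided alpha 0.05, 90% power, 31 per cell required (Sample Size and Power); 35 per cell planned (section 4.0); NDI MCID 5.5 to 7 points (NDI description, section 4.0).

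**Assumptions.** SD 12 also holds at 4 weeks; categorical time; complete data; the MCID and the SD are on the same NDI scale; the 4-week-only effects are illustrative.

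**1. The plan's figure.** n = 2σ²(z₀.₉₇₅ + z₀.₉₀)²/δ² = 2 × 144 × (1.960 + 1.282)²/100 = 30.3, so 31 per cell. It reproduces, for a two-cell difference at 1 week. (It follows from 10/12 = 0.833, not from the stated effect size of 0.80.)

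**2. Variance of the interaction contrast at one visit.** It combines four cell means: V = 4 × 144/n.
- n = 31: V = 18.58, SE 4.31
- n = 35: V = 16.46, SE 4.06

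**3. Correlation of the two changes.** Under a random intercept, a change has variance 2σₑ² = 144, so σₑ² = 72. The 1-week and 4-week changes share only the baseline error, so their covariance is 72 and their correlation is 72/144 = 0.5.

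**4. Joint 2-df test.** With interactions d₁ at 1 week and d₄ at 4 weeks, the noncentrality is λ = (d₁² − d₁d₄ + d₄²)/(0.75V). The last column is the 1-df test of the 1-week contrast.

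| (d₁, d₄) | n per cell | λ | Joint test rejects | 1-week contrast rejects |
|---|---|---|---|---|
| (0, 10) | 31 | 100/13.94 = 7.18 | 67% | 5% |
| (0, 10) | 35 | 100/12.34 = 8.10 | 72% | 5% |
| (0, 7) | 31 | 49/13.94 = 3.52 | 37% | 5% |
| (0, 7) | 35 | 49/12.34 = 3.97 | 41% | 5% |
| (0, 5.5) | 31 | 30.25/13.94 = 2.17 | 24% | 5% |
| (0, 5.5) | 35 | 30.25/12.34 = 2.45 | 27% | 5% |
| (10, 5) | 31 | 75/13.94 = 5.38 | 53% | 64% |
| (10, 5) | 35 | 75/12.34 = 6.08 | 59% | 69% |
| (10, 0) or (10, 10) | 31 | 7.18 | 67% | 64% |
| (10, 0) or (10, 10) | 35 | 8.10 | 72% | 69% |

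These use the large-sample chi-square. A noncentral F with 2 and 2(4n − 4) df lowers them by at most about one point (66% for (0, 10) at 31 per cell).

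**5. Checks.**
- Simulation of (0, 10) at 35 per cell, 20,000 runs: the joint test rejects in 72.1% and the 1-week contrast in 5.1%. In 67% of runs the joint test is significant and the 1-week contrast is not.
- Correlation 0.3 or 0.7 instead of 0.5, for (0, 10) at 35 per cell: 63% or 88%.
- Linear time, same case: 79% with times 0, 1, 4 and 69% with times 0, 1, 2. Linear coding does not remove the problem.

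**6. Size needed for the 1-week contrast.** For 10 points at 90% power, n = 4 × 144 × (1.960 + 1.282)²/100 = 60.5, so 61 per cell or 244 in total.

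**The case against.** The best defence is that 4 weeks is not an afterthought. It appears in the primary hypothesis in three places, so a test covering both visits could be what was meant. That stands as evidence that the documents are ambiguous about the target. It does not rescue the test: the hypothesis predicts benefit at 1 week and at 4 weeks, while the joint test is satisfied by either.

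Second, the 2-df reading is inferred. The sentence naming the 1-week scores follows directly after the interaction, so an intended 1-week reading is open. That too stands, and it makes this under-specification rather than a declared plan to test the wrong thing. But no 1-week contrast is written, and linear coding behaves no better.

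A reader might also infer three stronger things that the documents do not support:

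- *That the rule would be declared valid on a 4-week signal.* No success criterion is written. A significant test of the stated hypothesis is possible without any 1-week effect modification; what would be concluded from it is not stated.
- *That a 4-week-only effect would be hidden.* The pairwise comparisons are made at each follow-up, and Primary Aim #1 sets out an expected pattern across cells, including no difference by CPR status within MoE. The 1-week cell results would be visible, though they are not a test of effect modification and nothing makes the conclusion depend on them.
- *That the joint test loses power.* At correlation 0.5, (10, 5) is its worst case for a 10-point effect at 1 week. At (10, 0) and (10, 10) it does slightly better than the 1-week contrast.

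**Conclusion.** The concern holds as a mismatch between the stated test and the stated target. With no interaction at 1 week, the joint test rejects in 67% to 72% of trials if there is a 10-point interaction at 4 weeks, and in 24% to 41% if it is 5.5 to 7 points. A 1-week contrast would reject in 5%. These figures rest on the assumptions listed with the calculation; the 4-week-only pattern is a scenario, not a forecast. The joint test is not faulty as a test of its own null: with no interaction at either visit it rejects at about 5%. The case is about testing the right quantity and does not depend on power. It should be settled before the data are examined, because it decides what a positive primary result means.

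**What to change.** In Primary Aim #1, replace the sentence on the hypothesis of interest with wording such as:

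> The primary test is the single-degree-of-freedom contrast on NDI at 1 week: (MTE minus MoE change in CPR-positive patients) minus (MTE minus MoE change in CPR-negative patients). It is estimated from the planned mixed model with time as a categorical factor, reported with its 95% CI and tested two-sided at 0.05. The same contrast is then tested in fixed order for NPRS at 1 week, NDI at 4 weeks and NPRS at 4 weeks, each only if the one before is significant.

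NDI goes first because the sample size uses it and section 3.0 calls disability the primary outcome. The order of the later steps is the sponsor's choice, but NPRS must be placed explicitly, since both outcomes are now called primary. Keep the pairwise comparisons as description of the cell pattern. Reconcile the Synopsis, section 2.0 and the hypothesis text in Primary Aim #1 with the chosen order.

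The model, visits and data stay the same, so the analysis change is wording only. The cost is candour about power. In Sample Size and Power, state that 90% applies to a 10-point difference between two cells, and that power for a 10-point interaction at 1 week is about 64% at 31 per cell and 69% at 35. Reaching 90% would take about 61 per cell (244 in total). If the trial stays at 140, the estimate and its interval should carry the interpretation of a non-significant result.

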# 7. Contingency planning

This study has established contingency plans to address potential challenges, such as recruitment difficulties or staff changes, which could otherwise introduce bias. By planning for these possibilities, investigators aim to maintain consistency and reliability throughout the research process.

If approved through IRB, the research study would begin in January 2025 and conclude on 12/31/2026.

Tools and study measures will include standardized, published outcome assessments at each of the follow-up periods.

All subjects will complete several commonly used instruments to assess pain and perceived disability in patients with neck pain. There is no consensus in the literature about the ideal health related quality of life instrument to be used in patients with neck pain. Therefore, investigators will use the following spectrum of outcome measures in attempt to capture the effect of treatment on the level of the patient's perceived recovery, disability, pain, and functional limitations:

Neck Disability Index: The NDI is the most widely used condition-specific disability scale for patients with neck pain and consists of ten items addressing different aspects of function, each scored from 0-5, with a maximum score of 50 points. The score is then doubled and interpreted as a percentage of patient perceived disability. Higher scores represent increased levels of disability. The NDI demonstrates moderate to excellent test-retest reliability (ICC 0.64 - 0.88) and good construct validity. The minimum clinically important difference ranges from 5.5 to 7 points in those with neck pain. (See Appendix A)

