# Data Analysis:

Descriptive statistics, including frequency counts for categorical variables and measures of central tendency and dispersion for continuous variables will be calculated to summarize the data. Baseline demographic data will be compared across treatment groups. The investigators will compare baseline variables between groups by using independent t-tests or Mann–Whitney U tests for continuous data and chi-square tests of independence for categorical data. If analysis of baseline data suggests randomization did not reasonably control for potential confounders, those covariates will be included in models to adjust for confounding variables. If appropriate, statistical adjustments will be made for baseline characteristics that are significantly different between groups. An intention-to-treat analysis will be utilized, in which all participants will be analyzed in the group to which they were originally assigned. All drop-outs and the reason for dropping out of the study will be reported. An *a priori* alpha level of 0.05 will be used for all analyses. All data will be screened to ensure they meet the assumptions for the inferential statistical analyses described below. If they do not meet the necessary assumptions, appropriate nonparametric procedures will be utilized.

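### The hypothesis that MoE outcomes do not differ by CPR status has no margin or confidence-interval rule, so as written only a non-significant result could support it

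*Combined protocol and SAP*

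**What the plan says.** Section 7.0, Data Analysis, Primary Aim #1 fits random intercept mixed models for NPRS and NDI and names the three-way interaction of treatment group, CPR status and time as the hypothesis of interest. It adds "planned pairwise comparisons at each follow-up period by using the Bonferroni test of inequality". Earlier in the same section, an "alpha level of 0.05 will be used for all analyses". The paragraph closes with a further hypothesis: because the rule is thought specific to TJM, "outcomes among those receiving the MoE treatment would not differ on the basis of" CPR status. The documents give no margin, equivalence test or confidence-interval criterion for that statement, and no number of comparisons for the Bonferroni correction.

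The Sample Size and Power paragraph assumes a "standard deviation of change scores on the NDI of 12 points" and sizes the cells for a 10-point difference "with 90% power using a two-tailed hypothesis", arriving at 31 per cell; 35 per cell are to be recruited. In section 4.0 the NDI is scored out of 50 and also doubled to a percentage. The same entry says: "The minimum clinically important difference ranges from 5.5 to 7 points".

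**The concern.** A test of difference can reject equality or fail to reject it; it cannot establish equality. The MoE hypothesis is a statement of no difference, and the pairwise test that addresses it directly can agree with it only by being non-significant. The Bonferroni correction makes non-significance more likely, and so works in favour of this one hypothesis.

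The contrast bears on interpretation. Similar MoE outcomes in CPR-positive and CPR-negative patients would help to show that the rule picks out responders to TJM rather than patients who do well under any care. The cells were sized for 10 points, above the protocol's important difference of 5.5 to 7. An MoE difference large enough to matter could therefore go undetected and be reported as agreeing with the hypothesis.

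**Working it through.** **Inputs.** SD of change 12, design difference 10, two-sided alpha 0.05, power 90%, 31 per cell required (Sample Size and Power). 35 per cell recruited (section 4.0). Important difference 5.5 to 7 (section 4.0, Neck Disability Index). No dropout rate is given, so 31 to 35 evaluable per cell is used as the range; 31/35 is an 11.4% loss. The number of Bonferroni comparisons is not given. I show one (no correction), three (the contrasts named in the hypotheses) and six (all pairs of four cells); three and six are assumptions. A two-group comparison of change scores stands in for the mixed-model contrast, as in the plan's own calculation.

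**Plan's own figure.** n = 2 × (1.960 + 1.282)² × (12/10)² = 30.3, rounded up to 31 per cell. This reproduces.

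**Precision of the MoE contrast (CPR+ minus CPR-).** SE = 12 × √(2/n) = 3.05 for n = 31 and 2.87 for n = 35. The 95% CI half-width is t × SE: 2.000 × 3.05 = 6.1 and 1.995 × 2.87 = 5.7 points. That is about the size of the important difference.

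**Chance of a non-significant result, SD and important difference on the same scale.** The normal approximation is 1 - Φ(δ/SE - z). For δ = 7, n = 35, no correction: 7/2.87 = 2.44, 2.44 - 1.96 = 0.48, giving 32%. For δ = 5.5, n = 31, six pairs: 5.5/3.05 = 1.80, 1.80 - 2.64 = -0.83, giving 80%. The t-based values are:

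| True difference | n per cell | No correction | Three comparisons | Six pairs |
|---|---|---|---|---|
| 7 | 35 | 33% | 50% | 60% |
| 7 | 31 | 38% | 56% | 66% |
| 5.5 | 35 | 53% | 70% | 78% |
| 5.5 | 31 | 57% | 74% | 81% |

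**Mixed scales.** If the SD of 12 is in percent points and the important difference is on the 50-point scale, 5.5 to 7 becomes 11 to 14 percent points. The t-based chance of non-significance runs from 0.2% (14 points, n = 35, no correction) to 19% (11 points, n = 31, six pairs).

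**What an equivalence rule would deliver.** Take two one-sided tests at 5%, equivalent to requiring the 90% CI to lie within ±m, with a true difference of zero. The normal approximation is 2Φ(m/SE - 1.645) - 1. For m = 7, n = 35: 2Φ(0.80) - 1 = 57%. The t-based values for n = 31 to 35 are 47-56% for m = 7 and 12-20% for m = 5.5. On the mixed-scale reading (m = 11 to 14) they are about 95% to 99.9%.

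**The case against.** The strongest reply is that the specificity question already has a formal test, the three-way interaction. A reader might infer that the pairwise comparison is the plan's only tool, or that a rule marking good prognosis under any treatment could easily be declared TJM-specific. The documents do not support either. A purely prognostic rule gives zero interaction, so the interaction test would flag it only at about the 5% level. If the treatments are otherwise equal, such a rule would also fail the required comparison of TJM with MoE in CPR-positive patients. If TJM is better for everyone, that comparison does not protect, but the interaction still does. The Synopsis and sections 1.0 and 2.0 define validity by the two superiority comparisons alone; the MoE statement appears only in section 7.0, as an expected corollary. All of this stands, and it makes the MoE contrast supportive.

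It does not rescue the MoE hypothesis itself. The interaction is the CPR difference under MTE minus the CPR difference under MoE, so a non-zero interaction is compatible with a sizeable MoE difference.

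A reader might also infer that the plan will accept non-significance as proof. No sentence says so; the investigators only hypothesize no difference. The point rests on the absence of any other criterion. Nor is the range of a third to four-fifths an unconditional miss rate. It needs a shared scale, and its upper end also needs 31 per cell, a 5.5-point difference and six pairs together.

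**Conclusion.** The point holds as a gap in the analysis wording. A no-difference hypothesis sits within the primary aim without a margin or interval rule, and a non-significant pairwise test would not be evidence for it on any scale. This does not undermine the interaction test or the two superiority comparisons.

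The size is conditional. For 1-week NDI with SD 12 and 31 to 35 per cell, an important MoE difference would be non-significant in about 33-57% of trials unadjusted and 60-81% with six-pair Bonferroni, if the SD and the important difference are on the same scale. It would be at most about 19% if the SD is in percent points and the important difference is on the 50-point scale. The documents do not settle which reading is right. The figures do not extend to NPRS, the other primary outcome, for which the documents give neither an SD nor an important difference.

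**What to change.** Amend Primary Aim #1 in section 7.0 as follows.

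- State whether NDI scores, the SD of 12 and the important difference are on the 50-point or the percent scale.
- Report the MoE difference, CPR-positive minus CPR-negative, at 1 week with its CI.
- Claim no difference in NDI only if the 90% CI lies within a prespecified margin chosen from the protocol's 5.5 to 7 point range and expressed on the stated scale. Otherwise report the comparison as inconclusive.
- Keep the specificity conclusion on the interaction already named, reported as the 1-week estimate with its CI, and label the MoE contrast supportive.
- For NPRS, report the contrast with its CI and draw no no-difference conclusion from non-significance.

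The cost is a few sentences, with no change to recruitment or conduct. The downside is that on the same-scale reading the claim will often be inconclusive even when the true difference is zero: equivalence would be shown in about 47-56% of trials at a margin of 7 and 12-20% at 5.5. On the mixed-scale reading the planned cells suffice (about 95% or more).

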# Secondary Objectives:

- To compare the long-term (6-month follow-up) clinical outcomes and healthcare utilization based on status on the CPR and the treatment received. The investigators hypothesize that patients who are positive on the CPR and receive TJM will demonstrate improved disability and lower health care utilization than patients who are negative on the CPR and receive TJM and compared to patients who are positive on the CPR but receive an alternative exercise program without TJM.
- 2. Compare changes in pain and fear-avoidance beliefs at long-term follow-up (6-month follow-up) based on status on the CPR and the treatment received. The investigators hypothesize that patients who are positive on the CPR and receive TJM will achieve greater improvement in 6-month pain levels and a reduction in fear-avoidance beliefs compared to patients who are negative on the CPR and receive TJM and compared to patients who are positive on the CPR but receive an alternative exercise program without TJM.

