The investigators will also examine healthcare utilization using a two-way ANOVA comparing the number of healthcare visits post-treatment sessions with treatment group (MTE vs. MoE) and status on the clinical prediction rule (positive or negative) as independent variables. If appropriate, the interaction effect of the two independent variables will also be accounted for in the analysis. The dependent variable is the number of healthcare visits after completion of the treatment. The investigators hypothesize that patients who are positive on the rule and received TJM utilize less additional healthcare visits after completion of the treatment than patients who are negative on the rule and received the MoE program without TJM.

Secondary Aim #2: To compare changes in GROC and fear-avoidance beliefs at long-term follow-up (6-month) based on status on the clinical prediction rule and the treatment received. The investigators will examine this with separate random intercept linear mixed models with treatment group (MTE vs. MoE), status on the clinical prediction rule (positive or negative), and time (baseline and 6-months) as fixed effects. The dependent variables will be GROC changes and fear avoidance beliefs. The hypothesis of interest is the group \* status on CPR \* time interaction. The investigators will perform planned pairwise comparisons at each follow-up period by using the Bonferroni test of inequality. The investigators hypothesize that patients who are positive on the rule and received TJM would experience greater reduction in pain and fear avoidance beliefs than patients who are negative on the rule and received TJM, compared with patients who are positive on the rule but received the MoE program without TJM.

Missing Data. While analysis using mixed models allows all observed data to be included in the analysis under the assumption that the data are missing at random, if substantial missing data occurs, multiple imputation or mean conditional imputation will be used with subsequent sensitivity analyses to explore the impact of imputation on results. To address the issue of artificially reduced estimates of stochastic uncertainty produced by imputation, bootstrapping procedures will be used on the entire imputation and estimation process.

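### Healthcare visits, a count, go into a two-way ANOVA with an optional interaction, and Sections 2.0 and 7.0 name different contrasts for them; settle the contrasts and use a negative binomial model that always keeps the interaction

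*Combined protocol and SAP*

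**What the plan says.** Section 7.0, Data Analysis, Secondary Aim #1 sets the outcome: "The dependent variable is the number of healthcare visits after completion of the treatment". The method is a "two-way ANOVA comparing the number of healthcare visits post-treatment sessions", with treatment group (MTE, which contains TJM, or MoE, which does not) and CPR status as factors. On the interaction it says: "If appropriate, the interaction effect of the two independent variables will also be accounted for in the analysis". It gives no rule for deciding what is appropriate.

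The general text of the same section sets an "alpha level of 0.05 will be used for all analyses" and provides a fallback after screening of the data: "If they do not meet the necessary assumptions, appropriate nonparametric procedures will be utilized". No procedure is named for a two-factor design.

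The hypothesis for visits is stated twice, differently:

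- Section 2.0, Secondary Objectives: CPR-positive patients given TJM will have "lower health care utilization than patients who are negative on the CPR and receive TJM", and also lower use than CPR-positive patients without TJM. These are two contrasts, each changing one factor.
- Section 7.0: the same patients will "utilize less additional healthcare visits after completion of the treatment than patients who are negative on the rule and received the MoE program". This is one diagonal contrast, changing both factors at once.

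No expected visit rate, dispersion or power is given for this outcome.

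**The concern.** A visit count cannot be negative and its variance usually rises with its mean. A pooled-variance ANOVA then applies one error estimate to cells whose spread differs whenever their means differ. The cell of most interest, CPR-positive with TJM, is the one expected to have the lowest count.

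The optional interaction is the larger matter. If it is left out, the model forces the treatment difference to be the same in both CPR strata. For the primary outcomes the plan argues the opposite: rule status should matter under TJM and not under MoE. If visits follow that pattern, an additive model averages a real effect with a null one. Whether this harms the planned comparison depends on which of the two stated hypotheses is meant. As written, the decision on the term could also be made after the data are seen.

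**Working it through.** **The plan's own figure.** The only sample size calculation is for NDI change at 1 week: a 10-point difference, SD 12, two-sided 0.05, "with 90% power using a two-tailed hypothesis". The normal approximation gives n = 2(1.960 + 1.282)² × 12²/10² = 30.3, so 31 per cell, as stated. It says nothing about visits. The plan recruits 35 per cell.

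**Dropping the interaction: algebra.** Let the cell means be a (CPR+/MTE), b (CPR+/MoE), c (CPR-/MTE) and d (CPR-/MoE), with equal cell sizes. The additive model estimates:

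- treatment effect, in either stratum: g = ½[(a - b) + (c - d)]
- CPR effect, under either treatment: s = ½[(a - c) + (b - d)]
- diagonal contrast: g + s = a - d, exactly the difference in cell means

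Take an assumed TJM-specific effect, a = 1.5 and b = c = d = 3. The true value of each Section 2.0 contrast is -1.5. The additive model gives ½(-1.5 + 0) = -0.75 for each, half the truth. The Section 7.0 contrast is unchanged at -1.5.

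**Dropping the interaction: simulation.** Counts are negative binomial with variance μ + αμ². The means and α are assumptions. For CPR+/MTE versus CPR+/MoE:

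| CPR+/MTE mean; other three cells | n per cell | Coverage of the additive model's 95% interval, over α = 0.5 to 2 |
|---|---|---|
| 1.5; 3 | 35 | 57% to 79% |
| 0.7; 2 | 31 | 48% to 72% |
| 1; 3 | 31 | 37% to 69% |

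In the first setting, power for this contrast falls from 72/51/29% with the full model to 41/29/18% with the additive model (α = 0.5/1/2).

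**Keeping the interaction: interval width.** With means 1.5/3/3/3, α = 1 and n = 35, the cell variances are 1.5 + 2.25 = 3.75 and, three times, 3 + 9 = 12. Their average is (3.75 + 36)/4 = 9.94.

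- Pooled SE of any two-cell difference: √(2 × 9.94/35) = 0.75
- True SD, CPR+/MTE versus CPR+/MoE: √((3.75 + 12)/35) = 0.67, so the interval is too wide
- True SD, CPR-/MTE versus CPR-/MoE: √(24/35) = 0.83, so the interval is too narrow

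In simulation with unequal means, nominal 95% intervals covered about 96-99% for the CPR+ treatment contrast and 90-94% for the CPR- one. The diagonal contrast went either way: 96-98% when only CPR+/MTE is low, 92-94% with graded means.

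**Keeping the interaction: error rate and power.** With equal means, ANOVA rejects in about 4-6% of trials and the negative binomial Wald test in about 5-7%. Power, ANOVA then negative binomial (means in the order a/b/c/d):

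| Contrast | Assumed means | n per cell | α = 0.5 | α = 1 | α = 2 |
|---|---|---|---|---|---|
| CPR+/MTE vs CPR-/MoE | 1.5/3/3/3 | 35 | 72, 83% | 51, 67% | 30, 47% |
| CPR+/MTE vs CPR-/MoE | 1.5/2.5/2.5/4 | 35 | 99, 99% | 91, 93% | 71, 75% |
| CPR+/MTE vs CPR+/MoE | 0.7/2/2/2 | 31 | - | 67, 86% | 44, 69% |
| CPR+/MTE vs CPR+/MoE | 1.5/2.5/2.5/4 | 31 | - | 17, 36% | 10, 26% |

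Across all patterns tried, the loss for the Section 7.0 contrast ran from about 0-6 points with graded means to about 30 points with one low cell.

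**The fallback.** In the first row's setting, Mann-Whitney power for the diagonal contrast was 74/54/31%, about the same as ANOVA. The usual rank tests also do not test a two-factor interaction.

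**The case against.** The best defence is that the ANOVA does little harm to the hypothesis written beside it. For CPR+/MTE versus CPR-/MoE, omitting the interaction costs essentially nothing, type I error stays near 5%, and with graded means the power loss is small. The plan also undertakes to check assumptions. All of this stands, except that the fallback names no two-factor method and so does not settle what would be done.

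A reader might infer that the interaction is itself the hypothesis for visits. The documents do not say so. They name an interaction as the hypothesis of interest for the mixed-model outcomes only; for visits they state cell contrasts.

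A reader might also infer that ANOVA always has less power for the interaction. The two models test different interactions, one of differences and one of ratios. With means 1/2/2/4, the ratios agree (1/2 = 2/4), so there is no ratio interaction, but (1 - 2) - (2 - 4) = 1 on the difference scale. There ANOVA's interaction power is 9-23% against 5-7%. Changing the model changes the question, so interaction-test power is not a fair basis for choosing between them.

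Finally, the negative binomial Wald test is slightly liberal, so a small part of its gain is not real.

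**Conclusion.** The point holds in a limited form. The plan leaves open both which contrasts are tested for visits and whether the model can estimate them.

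- **Interaction dropped, TJM-specific effect:** the Section 2.0 contrasts are about halved, with 37-79% coverage. The Section 7.0 contrast is essentially untouched; this is exact with equal cells.
- **Interaction kept:** the test is valid at 5%. Intervals are modestly too wide around the low-count cell and modestly too narrow between higher-count cells. Power loss is negligible to about 30 points, depending on the contrast, means and dispersion.

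A reader might take a large power loss, or seriously wrong error bars, as established. Neither is: every visit mean and dispersion used here is assumed, and with the full model the interval error is modest. The outcome is secondary with no stated power, and neither the primary analysis nor the sample size is affected. The change is still worth making, because a model that always keeps the interaction can estimate either set of contrasts and removes a choice that could depend on the data.

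**What to change.** 1. Reconcile Sections 2.0 and 7.0 and state which cell contrasts are tested for healthcare visits.
2. Replace the ANOVA with a negative binomial model for visits after completion of treatment that always contains treatment, CPR status and their interaction.
3. Add log follow-up time as an offset. Section 3.0 collects use at 3 and 6 months, so a participant who answers only at 3 months contributes a count over a shorter period, which an ANOVA of raw counts ignores.
4. Report the pre-specified contrasts as rate ratios with 95% confidence intervals, beside model-based mean visits and mean differences for the cells. Rest inference on these contrasts and not on the interaction test.

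The cost is a few sentences in Section 7.0, plus alignment with Section 2.0; visits, sample size and data collection do not change. The real downside is that the main effect measure moves to the ratio scale, so the model's interaction term no longer answers the question that the ANOVA interaction would. Mean visits per cell keep the absolute difference in view.
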